### **3.5.6 Restrictions**

#### **3.5.6.1 Prior Therapy and Prohibited Medications**

Medication(s) that when co-administered with an sGC stimulator could increase the risk of hypotension are prohibited from 6 days before Check-in through the End of Trial Visit. These medications include (but may not be limited to) nitrates, nitroglycerin, direct vasodilators (including hydralazine or systemic minoxidil), or phosphodiesterase (PDE) 5 inhibitors (including sildenafil, tadalafil, and vardenafil), alpha adrenergic blockers, riociguat, and sodium-glucose co-transporter 2 (SGLT2) inhibitors.

### **3.5.6.2 Vitamins and Supplements**

All vitamins and herbal supplements are prohibited within 7 days before Check-in through the End of Trial Visit. Supplements for the treatment of erectile dysfunction are prohibited within 14 days before Check-in through the End of Trial Visit.

### **3.5.6.3 Fluid and Food Intake and Nicotine-containing Product Use**

The following food, fluid, and tobacco restrictions apply:

- All nicotine-containing products (eg, cigarettes, e-cigarettes, vape pens, cigars, chewing tobacco, gum, patches) are prohibited within 6 months before Check-in through the End of Trial Visit.
- All alcohol-containing foods or beverages are prohibited within the 7 days before Check-in through Discharge.
- Patients may consume up to 2 cups of coffee or tea per day but not within 1 hour of study drug administration or within 3 hours before EndoPAT assessments.
- Grapefruit and grapefruit juice are prohibited within 72 hours before Check-in through the End of Trial Visit.
- Food is not allowed for 8 hours before study drug administration. Breakfast should begin within 30 minutes of study drug administration.
- Food is not allowed 8 hours before clinical laboratory sample collections.
- While in clinic, patients will follow a standard diet for diabetics.

Because poppy seeds can sometimes cause a positive result on the drugs of abuse test, subjects are advised to avoid eating poppy seeds or foods containing poppy seeds for at least 48 hours before the drug screen at the Screening Visit, Check-in, and Follow-up Visit.

The subject's food consumption will be recorded in the subject's source documentation.

### **3.5.6.4 Patient Activity Restrictions**

The following subject activity restrictions apply:

- Subjects are not to donate blood within the 6 weeks before Check-in.
- Subjects are not to have received blood products within the 2 months before Check-in.

- Subjects are not to have undergone a surgical procedure (other than minor dermatologic procedures) during the 30 days before Check-in.
- Subjects should refrain from making any major lifestyle changes (eg, changing his or her exercise pattern) from the time of signature of the ICF to the End of Trial Visit.
- Female subjects are not breastfeeding.

### **3.6 STOPPING CRITERIA**

All dosing will be stopped if the Sponsor and Investigator determine that any of the following have occurred:

- Drug-related SAEs in 2 or more patients (per causality and SAE definitions in the protocol)
- An overall pattern of clinically significant AEs or an overall pattern of patient tolerability issues, which may appear minor in terms of an individual event but, in the opinion of the Sponsor or Investigator, collectively represents a safety concern

Note: Safety and tolerability will be assessed daily and dosing may be discontinued or dose escalation may be cancelled on an individual patient basis. Patients who discontinue dosing or do not escalate will remain in the clinic for at least 24 hours after their final dose of study drug and will complete all Discharge day assessments. In addition, these patients will return to the clinic for their Follow-up and End of Trial Visits 14 ( $\pm 2$ ) and 28 ( $\pm 3$ ) days, respectively, after their final dose of study drug.

### **3.7 STUDY PROCEDURES**

#### **3.7.1 Informed Consent**

Informed consent procedures will comply with the Code of Federal Regulations (CFR) 21, Parts 50 and 312.

The written ICF must be approved by the Institutional Review Board (IRB) for the purposes of obtaining and documenting consent.

Before entry into the study, each patient will be provided with a written explanation of the study. It is the responsibility of the Investigator or appropriately trained health professional to give each

patient full and adequate information regarding the objectives and procedures of the study and the possible risks involved. Patients will then be given the opportunity to ask questions and the Investigator will be available to answer questions as needed. Patients will be informed of their right to withdraw from the study at any time without prejudice. After this explanation and before entering the study, the patient will voluntarily sign an ICF. The patient should receive a copy of the signed and dated ICF. The Investigator must retain each patient's original signed ICF.

If new information becomes available that may be relevant to the patient's consent and willingness to participate in the study, the ICF will be revised. The revised ICF must be submitted to the IRB for review and approval prior to its use.

### **3.7.2 Medical History**

A complete medical history will be recorded at the Screening Visit.

### **3.7.3 Safety Assessments**

#### **3.7.3.1 Physical Examination**

A complete physical examination will be performed according to the Schedule of Events. The physical examination of each patient should include examination and assessment of the following:

General appearance	Lymph nodes	Musculoskeletal system
Cardiovascular system	Neurologic status	Nervous system
Respiratory system	Head, eyes, ears, nose, and throat	Skin
Abdomen/liver/spleen	Neck	Mental status

Breast, genitourinary, and rectal examinations are optional and may be performed at the discretion of the Investigator. Any new, clinically significant abnormal findings from the physical examination will be reported as an AE.

Height will only be recorded at the Screening Visit; weight will be recorded according to the Schedule of Events.

### **3.7.3.2 Vital Signs**

Vital signs will be measured according to the Schedule of Events and documented on the eCRF. Vital sign measurements include oral temperature (°C), respiratory rate, and supine and standing BP and pulse. Respiratory rate will be taken after the patient has been seated for at least 5 minutes. At the Screening Visit and at Check-in, the blood pressure assessments should be completed at medication trough level, i.e. prior to subjects taking their hypertensive medications. In addition, at the Screening Visit and at Check-in the supine BP measurements will be the average of 3 measurements obtained at 2-minute intervals after the patient has been lying quietly for at least 5 minutes; for supine only BP and pulse measurements thereafter, patient must lie quietly for at least 5 minutes before measurements are taken. For supine and standing BP and pulse measurements, patient must lie quietly for at least 5 minutes before supine measurements are taken, then assume a sitting position for 1 minute, and finally assume a standing position for 2 minutes before standing measurements are taken. All BP and pulse measurements should be taken in the arm not used for EndoPAT occlusion and before blood draws where applicable.

### **3.7.3.3 Electrocardiograms**

A 12-lead ECG will be performed according to the Schedule of Events and documented on the eCRF. Electrocardiograms should be obtained after the patient has been supine for at least 5 minutes. (Note: if on initial ECG, QTcF is  $\geq 450$  msec for male patients or is  $\geq 470$  msec for female patients, the ECG will be repeated 2 more times, and the average of the 3 QTcF values will be used to determine the patient's eligibility.)

### **3.7.3.4 Clinical Laboratory Tests**

Blood and urine samples for clinical laboratory tests will be collected, preferably from the left arm, according to the laboratory study procedures at the days and times defined in the Schedule of Events. Patients must have fasted for at least 8 hours before sample collections. The clinical laboratory evaluations will include the serum chemistry, hematology, coagulation, and urinalysis panels and the additional tests presented in Table 2.

**Table 2. Clinical Laboratory Tests**

Serum Chemistry Panel	Hematology Panel (CBC)	Complete Urinalysis
Albumin	Hematocrit	Color and appearance
Alkaline Phosphatase	Hemoglobin	pH and Specific Gravity
ALT	Platelet count	Bilirubin
AST	MPV	Glucose
Bicarbonate	RBC count	Ketones
BUN	WBC count	Leukocytes
Calcium	WBC differential	Nitrates
Chloride	(% & absolute):	Occult blood
Cholesterol	Basophils	Protein
Creatinine	Eosinophils	Urobilinogen
GGT	Lymphocytes	Microscopic
Glucose	Monocytes	Including bacteria, RBCs, WBCs per HPF if dipstick is abnormal
HDL-c	Neutrophils	
LDH	RBC indices	
LDL-c (calculated)	MCH	Additional tests
Magnesium	MCHC	Hemoglobin A1c
Phosphorus	MCV	Fasting blood glucose
Potassium	RDW	Serum insulin
Sodium		
Total Bilirubin	Coagulation Panel	
Total Protein	aPTT	
Triglycerides	Prothrombin time	
Uric acid	INR	

ALT = alanine aminotransferase; aPTT = activated partial thromboplastin time; AST = aspartate aminotransferase; BUN = blood urea nitrogen; CBC = complete blood count; GGT = gamma glutamyl transferase; HPF = high power field; INR = International Normalized Ratio; LDH = lactate dehydrogenase; MCH = mean corpuscular hemoglobin; MCHC = mean corpuscular hemoglobin concentration; MCV = mean corpuscular volume; MPV = mean platelet volume; RBC = red blood cell; RDW = red blood cell distribution width; WBC = white blood cell.

For female patients, a negative serum pregnancy test must be documented at the Screening Visit, at Check-in with results available before dosing, and at the End of Trial Visit; a negative urine pregnancy test must be documented at the Follow-up Visit before nitroglycerin dosing. In the event of a positive pregnancy test, the test will be repeated. If pregnancy is confirmed, see Section 3.7.3.8.

At the Screening Visit, blood will be collected for a hepatitis panel (including hepatitis B surface antigen [HBsAg] and anti-hepatitis C virus [HCV]) and human immunodeficiency virus (HIV) antibody screen.

A urine drug screen for selected drugs of abuse and an alcohol breathalyzer screen will be performed at the Screening Visit, Check-in, and the Follow-up Visit. Patients will be screened for the following drugs of abuse:

Amphetamines	Cocaine	Opiates
Barbiturates	Cotinine	Phencyclidine (PCP)
Benzodiazepines	Marijuana	Propoxyphene

### 3.7.3.5 Adverse Events

All patients will be monitored for AEs throughout the study. All AEs will be recorded in accordance with the procedures outlined in this section.

An AE is any untoward medical occurrence in a patient or clinical investigation subject administered a pharmaceutical product and which does not necessarily have to have a causal relationship with this treatment.

An AE, therefore, can be any unfavorable and unintended sign (including an abnormal laboratory finding, for example), symptom, or disease temporally associated with the use of a medicinal product, whether or not considered related to the medicinal product.

An AE includes, but is not limited to, the following:

- Any unfavorable changes in general condition
- Any clinically significant worsening of a preexisting condition
- Any intercurrent diseases and accidents

**Note:** A procedure is not an AE, but the reason for a procedure may be an AE.

### 3.7.3.5.1 Causality Assessment

For all AEs, the Investigator must provide an assessment of causal relationship to study drug. The causality assessment must be recorded in the patient's source documentation and on the AE page of the subject's eCRF. Causal relationship must be assessed according to the following:

**Related:** An event where there is a reasonable possibility of a causal relationship between the event and the study drug

**Unrelated:** Any other event

### 3.7.3.5.2 Severity Assessment

The Investigator will provide an assessment of the severity of each AE by recording a severity rating in the patient's source documentation and on the AE page of the patient's eCRF. *Severity*, which is a description of the intensity of manifestation of the AE, is distinct from *seriousness*, which implies a patient outcome or AE-required treatment measure associated with a threat to life or functionality. Severity will be assessed according to the following scale:

**Mild:** A type of AE that is usually transient and may require only minimal treatment or therapeutic intervention. The event does not generally interfere with usual activities of daily living.

**Moderate:** A type of AE that is usually alleviated with additional specific therapeutic intervention. The event interferes with usual activities of daily living, causing discomfort but poses no significant or permanent risk of harm to the research participant.

**Severe:** A type of AE that interrupts usual activities of daily living, or significantly affects clinical status, or may require intensive therapeutic intervention.

### 3.7.3.6 Serious Adverse Events

An SAE is defined as any AE occurring at any dose that results in any of the following outcomes:

- Death
- Life-threatening: the patient was at immediate risk of death from the reaction as it occurred (ie, it does not include a reaction that hypothetically might have caused death if it had occurred in a more severe form)

- Hospitalization or prolongation of existing hospitalization
- Persistent or significant disability/incapacity: a substantial disruption of a person's ability to conduct normal daily functions
- Congenital anomaly/birth defect
- Important medical events: events that may not result in death, be life threatening, or require hospitalization. Such an event may be considered serious when, based on appropriate medical judgment, it may jeopardize the subject and may require medical or surgical intervention to prevent 1 of the outcomes listed in this definition. Examples of such medical events include allergic bronchospasm requiring intensive treatment in an emergency department or at home, blood dyscrasias or convulsions that do not result in inpatient hospitalization, or the development of drug dependency or drug abuse.

Emergency room visits that do not result in admission to the hospital should be evaluated for 1 of the other serious outcomes (eg, life-threatening, other serious [medically important] event).

### **3.7.3.7 Recording Adverse Events**

Adverse events will be collected and recorded from the time the patient signs the ICF at the Screening Visit through the End of Trial Visit. All AEs, regardless of the assumption of a causal relationship with study procedures or study medication, must be recorded in the patient's source documentation and subsequently on the appropriate AE page of the patient's eCRF. This record includes AEs the patient reports spontaneously, those observed by the Investigator, and those elicited by the Investigator in response to open-ended questions during the study, such as "Have you had any health problems since your last visit?"

For every AE, the Investigator must

- Provide an assessment of the severity, causal relationship to the study medication, and seriousness of the event
- Document all actions taken with regard to the study medication (ie, no action taken, treatment temporarily interrupted, or treatment discontinued)
- Detail any other treatment measures taken for the AE, including concomitant medications and/or procedures

Pretreatment AEs will be collected from the time the patient signs the ICF until the patient receives study drug. Pretreatment AEs will be captured in the patient's source documentation but will only be entered for patients who receive study drug on the AE page of the patient's eCRF.

Laboratory abnormalities and changes in vital signs, physical examination findings, and 12-lead ECG parameters should be considered AEs and reported on the AE page of the patient's eCRF if the Investigator considers them clinically significant and/or they necessitate intervention.

Any medical condition that is present when a patient is screened and does not worsen in severity and/or frequency should be reported as Medical History and not as an AE. However, if the condition does deteriorate in severity and/or frequency at any time during the study, it should be reported as an AE.

### **3.7.3.8 Reporting Serious Adverse Events**

An AE that meets any of the serious criteria must be reported to Ironwood within 24 hours from the time that site personnel first learn of the event, using the SAE Report form provided for the study. Regardless of causality, all SAEs must be reported and will be collected and recorded from the time the subject signs ICF at the Screening Visit until the End of Trial Visit. All SAEs must also be recorded in the subject's source documentation and on the AE page of the subject's eCRF.

The initial report should include at least the following information:

- Patient identification number
- Description and onset of the event
- Serious criteria
- Causality assessment to study drug

### **Special Situation: Exposure to Study Drug during Pregnancy**

In the event that a pregnancy occurs in a patient, the study drug must be stopped at once, and study personnel must report the pregnancy as soon as possible (within 24 hours after notification) on the pregnancy notification form provided for this study. The study personnel must follow the

pregnancy until the end and report the pregnancy outcome on the pregnancy outcome form provided for this study. If the pregnancy is associated with an SAE (eg, if the mother is hospitalized), a separate SAE form must be completed.

All relevant SAE or pregnancy information should be emailed to Ironwood Drug Safety and Pharmacovigilance.

**All SAE Report Forms should be emailed to:**

Clinical Drug Safety & Pharmacovigilance  
Ironwood Pharmaceuticals, Inc.

If follow-up is obtained, or requested by Ironwood, the additional information should be emailed on an SAE Report Form to Ironwood, in a timely manner according to the procedures outlined above. Copies of discharge summaries, consultant reports, autopsy reports, and any other relevant documents may also be requested.

Appropriate remedial measures should be taken by the Investigator using his/her best medical judgment to treat the SAE. These measures and the subject's response to these measures should be recorded. All SAEs regardless of relationship to study drug will be followed by the Investigator until satisfactory resolution, until the Investigator deems the SAE to be chronic or stable, or until the subject is lost to follow-up. Clinical, laboratory, and diagnostic measures should be employed by the Investigator as needed to adequately determine the etiology of the event.

The Investigator will be responsible for reporting all SAEs to the IRB. Ironwood will be responsible for reporting to the regulatory authorities.

**3.7.4 Pharmacodynamic Assessments**

Hemodynamic and endothelial function assessments will be used to determine the PD parameters for PD analyses.

### **3.7.4.1 Hemodynamics**

Blood pressure and pulse measurements for PD analyses will include supine and standing pulse and BP (for calculation of orthostatic pulse rate and BP) and ABPM collected according to the Schedule of Events. The left arm will be used for BP measurements. Hemodynamic effects will be assessed using the following parameters:

- From supine and standing measurements – change from baseline (placebo cycle) in systolic and diastolic BP and pulse rate measurements
- From orthostatic (standing minus supine) measurements – orthostatic change in systolic and diastolic BP and pulse rate
- From ambulatory monitoring – change from baseline (placebo cycle) in 4-hour, 30-minute, and daytime (awake) averages of systolic and diastolic BP, mean arterial pressure, and pulse rate

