## **Criteria for Evaluation**

### ***Pharmacodynamics***

#### **Hemodynamics**

Supine and standing pulse and BP measurements and ambulatory pulse and BP monitoring will occur according to the Schedule of Events. Hemodynamic effects will be assessed using the following parameters:

- From supine measurements – change from baseline (placebo cycle) in systolic and diastolic BP and pulse rate measurements
- From orthostatic (standing minus supine) measurements – orthostatic change in systolic and diastolic BP and pulse rate
- From ambulatory monitoring – change from baseline (placebo cycle) in 4-hour, 30-minute, and daytime (awake) averages of systolic and diastolic BP, mean arterial pressure, and pulse rate

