#### ***Pharmacodynamic Analyses***

Summary statistics will be provided by treatment for RHI (from EndoPAT); supine, standing, and ambulatory BP and pulse rate values; and platelet function testing (from PFA-100). Changes from baseline (placebo cycle) in these variables will be compared across dose levels.

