#### **3.9.3.3 Pharmacodynamic Analyses**

##### **3.9.3.3.1 Hemodynamics**

Descriptive statistics including 95% confidence intervals will be presented for the following hemodynamic parameters by treatment group:

- Change from study baseline (Day -1 assessment) and time-matched baseline (placebo cycle assessments) in supine pulse, systolic BP, and diastolic BP
- Orthostatic change in pulse, systolic BP, and diastolic BP. An orthostatic measurement is obtained by subtracting the supine measurement from the standing measurement
- Change from time-matched baseline (placebo cycle assessments) in 4-hour, 30-minute, and daytime averages of systolic BP, diastolic BP, mean arterial pressure and pulse measurements from ambulatory BP monitoring
- Change from pre-nitroglycerin dose assessment to post-nitroglycerin dose assessment in supine pulse, systolic BP, and diastolic BP

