7.7 PHARMACODYNAMIC (PD) ANALYSIS

7.7.1 PD Parameters

The pharmacodynamic parameters are described below:

Ambulatory BP Monitoring

- Change from time-matched baseline in average daytime systolic BP, MAP, diastolic BP, and pulse. The daytime average for any IW-1973 cycle is defined as the average of the 30-minute average ambulatory assessments from the time of dosing on the ABPM assessment day to the end of the 12-hour ABPM recording for that cycle. Time-matched baseline is defined as the average of ambulatory assessments from the time of dosing on the ABPM assessment day of the Placebo cycle (Study Day 2) to the end of the 12-hour ABPM recording.
- Change from time-matched baseline in average daytime systolic BP, MAP, diastolic BP, and pulse by race (blacks vs. non-blacks)
- Change from time-matched baseline in 4-hour averages of MAP, systolic BP, diastolic BP, and pulse. The 4-hour averages are calculated from the time of dosing on the ABPM assessment day, using the 30-minute average values. Baseline is defined as the corresponding 4-hour average on Day 2 of the placebo cycle.

- Change from time-matched baseline in systolic BP, diastolic BP, MAP, and pulse at 30-minute postdose intervals. See Section 9.7 for details on calculation of assessment time intervals. Baseline is defined as the corresponding 30-minute average on Day 2 of the placebo cycle.

Supine Pulse and BP Measurements

- Change from study baseline in supine systolic BP, diastolic BP, and pulse
- Change from time-matched baseline (placebo cycle) in supine systolic BP, diastolic BP, and pulse
- Change from cycle baseline in supine systolic BP, diastolic BP, and pulse
- Change from trough baseline in trough systolic BP, diastolic BP, and pulse. The trough value for each cycle is defined as the 24 hour postdose assessment after the last dose of that cycle. Trough baseline is the last assessment prior to initiation of IW-1973 administration, that is, the Study Day 4 predose assessment
- Change from pre- to post-nitroglycerine dose assessments of supine systolic BP, diastolic BP, and pulse at the follow-up visit

Orthostatic BP Measurements

- Orthostatic changes in systolic BP, diastolic BP, and pulse. An orthostatic measurement is obtained by subtracting the supine measurement from the standing measurement.

Endothelial Function Assessments

- Change from study baseline in RHI
- Change from time-matched baseline (placebo cycle) in RHI
- Change from cycle baseline in RHI

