7.7.2 PD Analysis

Descriptive statistics will be presented for the observed and change from baseline results for the PD parameters at each scheduled timepoint by cycle group. 95% confidence intervals of the mean difference will be included for summaries of change from baseline results.

For orthostatic BP parameters, descriptive statistics will be presented by cycle group for the change from supine to standing measurements at each scheduled timepoint.

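### No paired change from placebo is planned for standing or orthostatic blood pressure and pulse, and the protocol disagrees with itself on whether standing values should have one

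*Protocol*

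**What the plan says.** The protocol makes four statements about cuff blood pressure and pulse relative to the placebo cycle, and they fall into two pairs.

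- **Standing included.** Section 3.7.4.1 lists "From supine and standing measurements – change from baseline (placebo cycle"), for systolic and diastolic pressure and pulse rate. The synopsis, under Pharmacodynamic Analyses, names "supine, standing, and ambulatory BP and pulse rate values" among the variables to be summarised and adds: "Changes from baseline (placebo cycle) in these variables will be compared across dose levels".
- **Supine only.** The synopsis evaluation criteria, under Hemodynamics, list "From supine measurements – change from baseline (placebo cycle) in systolic and diastolic BP and pulse rate measurements". Section 3.9.3.3.1, which specifies the hemodynamic analyses, gives change from "time-matched baseline (placebo cycle assessments) in supine pulse, systolic BP, and diastolic BP".

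Wherever the protocol defines the orthostatic parameter, it is standing minus supine with no baseline.

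In SAP 7.7.1 the changes from study, time-matched, cycle and trough baseline for cuff readings are all for supine values. The orthostatic entry is "Orthostatic changes in systolic BP, diastolic BP, and pulse", and SAP 7.7.2 specifies its output: "For orthostatic BP parameters, descriptive statistics will be presented by cycle group for the change from supine to standing measurements". SAP 8, which records differences from the protocol, says nothing about standing values.

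**The concern.** Blood pressure, heart rate and tolerability are study objectives, and protocol 3.2 justifies the design by each patient acting as his or her own control. The SAP uses that control for supine and ambulatory readings but not for standing readings or for the fall on standing. A reader who wants to know how a dose changes the orthostatic response must compare separate cycle summaries, which carry no interval for the difference.

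Dropout adds to this. Protocol 3.6 lets escalation be cancelled for individual patients, 3.4.3 rules out replacement after dosing, and SAP 6.3 imputes nothing. The mean at a high dose may therefore come from fewer patients than the placebo mean beside it.

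**Working it through.** **1. Does another section supply the contrast?**

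- SAP 7.7.2 promises intervals for change-from-baseline results of the PD parameters. SAP 7.7.1 lists no such parameter for standing or orthostatic values, so the sentence does not reach them.
- SAP 6.1 attaches 95% intervals to continuous PD parameters, so each cycle's orthostatic mean may carry its own. Two single-cycle intervals do not give the interval for their difference.
- SAP 7.9.3 summarises vital signs left out of the PD analyses, and flags notable standing values, against study baseline. SAP 6.1 equates study baseline with Day -1, but the Check-in list in protocol 3.8.2.1 has supine blood pressure only. On that definition standing values have no scheduled reference.
- The orthostatic threshold counts in SAP 7.9.3 are given by cycle and are not contrasted with placebo.

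**2. Can it be computed?** Yes. Protocol 3.8.2.2 schedules supine-to-standing readings on the first day of every cycle, including placebo Day 1: predose and at 1, 2, 4, 8 and 12 h.

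**3. What would pairing gain?** The plan states no figure to reproduce; the sample size was set outside statistical considerations. Inputs: n = 12 (protocol); SD = between-patient SD at one timepoint, assumed equal in both cycles; rho = within-patient correlation between cycles, assumed.

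- Paired half-width = t(0.975, 11) × √(2(1 − rho)) / √12 = 2.201 / 3.464 × √(2(1 − rho)) = 0.635 × √(2(1 − rho)) SD.
- Independent means = t(0.975, 22) × √(2/12) = 2.074 × 0.408 = 0.85 SD.

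| rho | Paired (SD) | Independent (SD) | Ratio | Paired interval |
|---|---|---|---|---|
| 0 | 0.90 | 0.85 | 1.06 | 6% wider |
| 0.3 | 0.75 | 0.85 | 0.89 | 11% narrower |
| 0.5 | 0.64 | 0.85 | 0.75 | 25% narrower |
| 0.7 | 0.49 | 0.85 | 0.58 | 42% narrower |
| 0.8 | 0.40 | 0.85 | 0.47 | 53% narrower |

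The two are equal at rho = 1 − (0.847/0.635)²/2, about 0.11. At an assumed SD of 10 mmHg, the paired half-widths for rho 0.3, 0.5 and 0.7 are 7.5, 6.4 and 4.9 mmHg, against 8.5 mmHg.

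**4. What does dropout do to a contrast read from the tables?** With complete data, the difference of cycle means equals the mean paired difference. Suppose instead that there is no drug effect, that 2 of 12 patients are missing at a dose, and that their placebo orthostatic change is 10 mmHg lower than the others'. The difference of cycle means then shifts by 2 × 10 / 12 = 1.7 mmHg (4 missing: 3.3 mmHg). The paired estimate stays at 0.

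**The case against.** A reader might infer that the SAP dropped an analysis the protocol had promised. The documents do not support that. The narrowing to supine values is already in protocol 3.9.3.3.1 and in the synopsis criteria, and the SAP follows them. Nor did the protocol ever promise a placebo-corrected orthostatic change, so SAP 8 had nothing to declare for that part. What stands is the protocol's conflict with itself, which the SAP resolves without saying so.

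A reader might also infer that the orthostatic effect is never examined within patients. That is too strong. Standing minus supine is itself a within-patient difference, it is tabulated for every cycle including placebo, and subtracting the means gives a rough contrast. Only the paired estimate in matched patients and its interval are missing. Table specifications are in a separate document, which might contain them, but the SAP does not call for them.

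The trial is exploratory and descriptive. No error rate, sample size or stopping rule depends on this contrast. The documents show concern about hypotension but do not rank orthostatic hypotension above other hemodynamic risks. The gain also depends on a correlation nobody has stated. The orthostatic value is a difference of single readings, so the correlation may be low.

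**Conclusion.** The point holds as an inconsistency and a gap in estimation, not as a broken commitment. The protocol gives two incompatible lists of parameters, the SAP adopts the narrower one without comment, and neither document plans a placebo-referenced orthostatic change. As a result, standing and orthostatic readings get no paired drug-minus-placebo estimate or interval.

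The text comparison is firm. The size is illustrative: a gain of 11% to 53% in interval width over correlations of 0.3 to 0.8, and none at zero, assuming equal SDs and all 12 patients contributing. Protection against unequal dropout is a separate benefit.

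It would be wrong to read the added contrast as isolating the drug effect. Doses escalate in a fixed order with no concurrent control, so dose remains mixed with time in clinic.

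**What to change.** 1. Reconcile the synopsis evaluation criteria, the synopsis Pharmacodynamic Analyses text, protocol 3.7.4.1 and protocol 3.9.3.3.1, so that all four agree on whether standing values are included. Record the outcome in SAP 8.
2. Add to SAP 7.7.1 the change from time-matched placebo in standing systolic pressure, diastolic pressure and pulse, and in the standing-minus-supine difference of each. Describe the second set as an added analysis. Give paired 95% intervals by cycle at 1, 2, 4, 8 and 12 h postdose, with the number of matched patients.
3. Label the 0 h reading of each active cycle as reflecting the preceding cycle's dose, since it is taken before the new dose.

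The cost is programming and tables from data already scheduled: 6 variables × 5 doses × 5 times = 150 further descriptive intervals, unadjusted under SAP 6.6. They should be presented as estimation only, with the caveat about time in clinic. This is a cheap improvement.
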